9.2. Sample Size Determination

9.2.1. Sample Size Assumptions

The sample size of 300 participants (considering 256 evaluable participants and additional 44 subjects for drop-out) in a 1:1 ratio has been determined by the superiority testing of mepolizumab 100 mg SC vs. placebo, there will be 90% power to detect a 40% decrease in the exacerbation rate from 1.7 per annum (p.a.) on placebo to 1.02 p.a. on mepolizumab 100mg SC using a two sided 5% significance level. The calculation assumes the number of exacerbations per year follows a negative binomial distribution [Keene, 2007] with a dispersion parameter $k=0.8$.

During the blinded evaluation, the clinically significant exacerbations which had occurred during the treatment period were analyzed using a generalized linear model assuming a negative binomial distribution and covariates of baseline maintenance OCS therapy (OCS vs. no OCS), EOS level at screening (≥ 300 cells/ μ L vs. < 300 cells/ μ L), number of exacerbations in previous year (as an ordinal variable) and baseline disease severity (as % predicted FEV1). The blinded evaluation estimated, the overall event rate based on an assessment of blinded data was observed as 0.78 p.a., the dispersion was 2.0. This was lower than the expected overall event rate of the original study design assumptions.

This observed reduction for overall events at blinded evaluation can be explained by a reduction in exacerbation events during the COVID-19 pandemic, which was not unique in China, it is still expected that the treatment effect of Mepolizumab compared with placebo will be the same in Chinese SEA population as the original study design assumption. Therefore, according the formula [Friede, 2010]

$$\bar{\lambda} = (\lambda_T + \lambda_P)/2$$

where $\bar{\lambda}$ is the observed overall events rate based on an assement of blinded data, the λ_T and λ_P are the event rates in the treatment and placebo groups, and assuming the reduction in exacerbation rate with Mepolizumab will remain 40% under pandemic, the estimated event rates λ_T and λ_P for Mepolizumab 100mg SC and placebo are 0.975 and 0.585 p.a. respectively. On the other hand, there exists a difference for the estimate of dispersion when data is blinded or unblinded, so that the blinded dispersion estimate is adjusted by the difference between blinded and unblinded, which is $1.6=2.0 * (0.796 / 0.972)$, where the dispersion in MEA115588 study were 0.796 (unblinded) vs. 0.972 (blinded).

Therefore, based on the conclusion of the blinded evaluation, assuming a 40% decrease in the exacerbation rate from 0.975 per annum (p.a.) on placebo to 0.585 p.a. on mepolizumab 100mg SC will lead to a power of 66% implying a high false negative rate of 34% in China study. If there is a true reduction of 40% in exacerbation rate in Chinese patients, based on use of Bayesian dynamic borrowing with an initial weight of 0.5 on global MEA115588 study result, there will be 88.6% probability to achieve a positive result (equivalent to the power of the study).

The 40% reduction in exacerbation rate has been selected as reductions of this magnitude or greater have been seen in previous mepolizumab studies MEA112997 and MEA115588. However, it should be noted that a smaller reduction in exacerbations could be clinically significant. Under the same assumptions, there will be 99% probability of showing consistent trend, which is defined as the point estimation of rate ratio between Mepolizumab and placebo<1 in China study, with global MEA115588.

9.2.2. Sample Size Sensitivity

The sample size in Section 9.2.1 is based on an expected reduction in this rate for subjects treated with mepolizumab. If the expected reduction with mepolizumab differ then, at the given sample size there will be an effect on the probability of success of the study. Table 7 illustrates this effect on probability of success of varying reductions in rates with mepolizumab, assuming the sample size remains constant at 128 subjects in mepolizumab arm and 128 subjects in placebo arm, excluding the additional 44 subjects to account for early withdrawals from study treatment.

Table 7 Probability of meeting the success criterion conditional on various assumed true treatment effects

Reduction	45%	40%	35%	0
Probabilities of Success	94.6%	88.6%	80.0%	11.8%*

*The false positive rate is calculated as assumed true treatment effects is 0 between Mepolizumab and placebo.

In the Table 7 , the probabilities of meeting success are conducted under various assumed true treatment effects when overall event rate is fixed as 0.78 based on the blinded evaluation and dispersion is 1.6, e.g. when reduction is 40%, then the probability of success is calculated by the exacerbation rates for Mepolizumab 100mg SC and placebo as 0.975 and 0.585 p.a. respectively. Type I error is 11.8%, which is calculated when the event rate for each group is 0.78, adjusted dispersion is 1.6 based on analyses of blinded evaluation.

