A second vague distribution worth 2 subjects (one in each treatment arm) assuming no treatment effect in China will also be specified, to allow for the possibility that the global MEA115588 data do not provide relevant information about the treatment effect in Chinese patients. A normal distribution with mean zero and standard deviation 2.1256 will be used as vague prior for log rate ratio in BDB design, more details can be found in [Appendix 9 Section 12.9.2](#). A weighted combination of the ‘informative’ and ‘vague’ priors will be used to construct a robust mixture prior.

In the primary analysis, a prior weight of 50% is proposed for the informative component of the robust mixture prior, with the remainder of the weight (50%) placed on the vague component to reflect a conservative starting position regarding the assumed relevance of the global MEA115588 results to Chinese patients. See Statistical [Appendix 9 Section 12.9.2](#) for more details on the robust mixture prior and [Section 12.9.3](#) for details on the choice of prior weight.

Effective Sample Size

The updated weight itself is not directly interpretable as the fraction of the global MEA115588 study sample size that is borrowed. Instead, the effective sample size (ESS) borrowed from the global study can be quantified using the moment method implemented in RBesT R software package version 1.6.1, [Table 9](#) shows the expected value of the ESS borrowed from the global MEA115588 study for each treatment comparison when the true reduction in China is assumed to be 45%, 40%, 35% and 0 as the same with [Table 8](#).

Table 9 Expected Effective Sample Size borrowed per arm from the global MEA115588 study for a range of possible true treatment differences

	The true reduction			
	0	35%	40%	45%
Expected value of ESS borrowed per arm from the global MEA115588 study	-42	76	123	162

Maximum Detectable Value for Rate Ratio

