12.9.3. Choice of weights

The scientific grounds for expecting similar benefit: risk profile in China and global study patients justifies a high initial weight on the informative component. However, based on an extensive review of the impact of the prior weight specified for the global MEA115588 study (prior weights explored were: 0, 0.1, 0.2, ...0.9,1), a more conservative prior weight of 50% was felt to provide an acceptable trade-off between the risks of a false positive result and a false negative result, and to enable meaningful gains in precision due to borrowing information from the global study whilst ensuring that the prior does not dominate the posterior completely but allows the observed data in Chinese patients to contribute to the inference from the study.

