5.2. Sample Size Sensitivity

The sample size in Section 5.1 is based on an expected reduction in this rate for subjects treated with mepolizumab. If the expected reduction with mepolizumab differ then, at the given sample size there will be an effect on the probability of success of the study.

[Table 2](#) illustrates this effect on probability of success of varying reductions in rates with mepolizumab, assuming the sample size remains constant at 128 subjects in mepolizumab arm and 128 subjects in placebo arm, excluding the additional 44 subjects to account for early withdrawals from study treatment.

Table 2 Probability of meeting the success criterion conditional on various assumed true treatment effects

Reduction	0.45	0.4	0.35	0
Probabilities of Success	94.6%	88.6%	80.0%	11.8%*

*The probability of success will equal with Type I error when there is no treatment effect for Mepolizumab compared with placebo.

In the [Table 2](#), the probabilities of meeting success are conducted under various assumed true treatment effects when overall event rate is fixed as 0.78 based on the blinded evaluation and dispersion is 1.6, e.g. when reduction is 40%, then the probability of success is calculated by the exacerbation rates for Mepolizumab 100mg SC and placebo as 0.585 and 0.975 p.a. respectively. Type I error is 11.8%, which is calculated when the event rate for each group is 0.78, adjusted dispersion is 1.6 based on analyses of blinded evaluation.

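### The 11.8% type I error pairs the blinded event rate with a dispersion scaled down for a treatment effect that the null excludes; the matching figure is about 12.8%, and Table 9's expected ESS appears not to be an average

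*Protocol*

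**What the plan says.** Protocol 9.2.1 reports the blinded evaluation: "the overall event rate based on an assessment of blinded data was observed as 0.78 p.a., the dispersion was 2.0". It then says that "the blinded dispersion estimate is adjusted by the difference between blinded and unblinded", using the MEA115588 dispersions of 0.796 (unblinded) and 0.972 (blinded), and arrives at 1.6.

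Protocol 9.2.2, Table 7, fixes the overall rate at 0.78 and the dispersion at 1.6. It gives success probabilities of 94.6%, 88.6%, 80.0% and 11.8% for true reductions of 45%, 40%, 35% and 0. The footnote to the last value reads "The false positive rate is calculated as assumed true treatment effects is 0 between Mepolizumab and placebo", and the text below the table says "Type I error is 11.8%, which is calculated when the event rate for each group is 0.78, adjusted dispersion is 1.6". SAP 5.2, Table 2, repeats the figure ("Type I error is 11.8%, which is calculated when the event rate for each group is 0.78") with the footnote "The probability of success will equal with Type I error when there is no treatment effect for Mepolizumab compared with placebo".

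Protocol 9.4.1, Table 9, gives -42, 76, 123 and 162 for reductions of 0, 35%, 40% and 45%. The row is labelled "Expected value of ESS borrowed per arm from the global MEA115588 study". The text cites the moment method in RBesT but does not say whether the values are averages or are taken at one observed effect.

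Protocol 12.9.3 says that the 50% prior weight "was felt to provide an acceptable trade-off between the risks of a false positive result and a false negative result".

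**The concern.** A blinded fit has no treatment term, so any difference between the arms is absorbed into the dispersion. That is why a blinded estimate can exceed an unblinded one, and it is the only reason 9.2.1 gives for scaling 2.0 down. The scaling factor comes from a trial with a large effect (rate ratio 0.47 in Protocol Table 8). The null column assumes no effect and puts the blinded rate in both arms, so it has no between-arm component to remove. Table 7 re-splits the rate for each assumed effect but carries one dispersion through every column.

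The false-positive rate is the price of borrowing and one of the two risks that the prior weight was chosen to balance. Table 9 is the plan's account of how much would be borrowed. Readers will judge the design on these figures, so they should be consistent with their inputs and correctly labelled.

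**Working it through.** **Inputs.** 128 evaluable per arm and overall rate 0.78 (Protocol 9.2.2). Blinded dispersion 2.0 and factor 0.796/0.972 (9.2.1). Prior 0.5 × N(-0.7474, SD 0.1532) + 0.5 × N(0, SD 2.1256), and success if P(RR < 1) ≥ 0.95 (9.1, 9.4.1; SAP 4.2.1). One year of follow-up per evaluable subject is assumed.

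**Formulas.** Var(log RR) = (1/λT + 1/λP + 2k)/128. The posterior is the two-component normal mixture of SAP 4.2.1. Solve for the observed log rate ratio c at which the posterior probability equals 0.95. Then P(success) = Φ((c - log RR_true)/SE).

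**Step 1: reproduce the plan at k = 1.6.**
- 40% reduction (0.975 placebo, 0.585 mepolizumab): variance (1.7094 + 1.0256 + 3.2)/128 = 0.04637 and SE 0.2153. The critical rate ratio is 0.776 (stated MDV 0.776), success 88.4% (stated 88.6%), and frequentist power 66.0% (stated 66%).
- 45% and 35%: 94.4% and 79.7% (stated 94.6% and 80.0%).
- Null: variance (2.5641 + 3.2)/128 = 0.04503, SE 0.2122, c = -0.2521. Then Φ(-0.2521/0.2122) = Φ(-1.188) = 11.74%. With the unrounded dispersion, 2.0 × 0.796/0.972 = 1.638, it is 11.84%. The stated 11.8% is reproduced.

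**Step 2: which dispersion fits the null?** For two equal arms, by moments, k_pooled = k(1 + d²) + d², with d = (1 - RR)/(1 + RR). At RR = 1, d = 0 and k_pooled = k, so a blinded 2.0 implies a true 2.0.

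A simulation agrees (negative binomial counts, 0.78 in both arms, no covariates; 113 per arm is an assumption based on the 225-subject trigger). With true k = 2.0 the unblinded/blinded ratio is 0.99, and it is 1.00 at 5,000 per arm. The plan applies 0.82. With true k = 1.6 the blinded estimate averages 1.58 and reaches 2.0 or more in 13% of trials.

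**Step 3: null at k = 2.0.** Variance (2.5641 + 4.0)/128 = 0.05128, SE 0.2265, c = -0.2575 (rate ratio 0.773). Then Φ(-0.2575/0.2265) = Φ(-1.137) = **12.77%**. Direct negative binomial simulation (80,000 trials per setting) gives 13.2% at k = 2.0 and 12.0% at k = 1.6, with Monte Carlo SE about 0.1 point.

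**Step 4: the other columns under the same logic.** Inverting the identity, k = (2.0 - d²)/(1 + d²):

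| Reduction | d² | k | Success | Stated |
|---|---|---|---|---|
| 35% | 0.0450 | 1.87 | 78.2% | 80.0% |
| 40% | 0.0625 | 1.82 | 87.3% | 88.6% |
| 45% | 0.0843 | 1.77 | 93.8% | 94.6% |

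Away from the null the identity is only a guide. Applied to MEA115588 (0.796, rate ratio 0.47), it predicts a pooled value of 1.03, against the reported 0.972.

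**Step 5: Table 9.** Moment ESS borrowed per arm = 128 × Var(log RR)/Var_posterior - 128, at k = 1.6. For example, with the observed ratio set to the true one at 40%: 128 × 0.04637/0.02359 - 128 = 123.6.

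| | 0 | 35% | 40% | 45% |
|---|---|---|---|---|
| Protocol Table 9 | -42 | 76 | 123 | 162 |
| Observed ratio = true ratio | -41.7 | 76.3 | 123.6 | 163.0 |
| Sampling mean | -22 | 72 | 100 | 125 |
| Sampling median | -29 | 76 | 121 | 152 |

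Only the second row matches all four cells, each within about 1. No single rescaling of the means would do so: stated/mean is 42/22 = 1.9 at no effect and 76/72 = 1.05 at 35%.

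**The case against.** The null inputs are disclosed, and 11.8% follows from them. Holding nuisance parameters fixed across an operating-characteristics table and varying only the effect is a common convention, so 11.8% can be read as the value if the true dispersion is 1.6. That stands. A reader might infer that 11.8% is a miscalculation; the documents do not support that. The convention does not settle the matter, however, because 1.6 is not offered as a free assumption. It is derived from the blinded 2.0 by a correction that has no role when the arms are equal.

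The gap is also within the uncertainty of the inputs. The documents give no precision for 0.78 or 2.0, and a blinded 2.0 can arise by chance when the truth is 1.6. This stands too: 12.8% is as conditional on blinded point estimates as 11.8% is. The blinded fit also used covariates, which the dispersion simulation did not.

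Correcting only the null column would be selective. That is fair; Step 4 shows that the other columns would move by about 1 to 2 points.

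A reader might also infer that a type I error limit is breached. The plan sets none, says that no frequentist test will be performed, and already discloses a rate well above 5%.

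On Table 9, the single-value reading is an inference. It uses the China-study unit variance; with that of MEA115588, neither the single value nor the mean matches. The word expected could loosely mean anticipated, although in a statistical table it ordinarily means an average. The documents do not show how the row was computed.

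**Conclusion.** The concern holds in a narrow form. The null column of Protocol Table 7 and SAP Table 2 is correct for its stated inputs, but those inputs are mismatched. On the plan's blinded point estimates the consistent false-positive rate is about 12.8% (about 13% by simulation), roughly one percentage point above the stated 11.8%. This assumes 128 evaluable per arm with one year each, and takes 0.78 and 2.0 at face value.

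Table 9 very probably shows the ESS when the observed rate ratio equals the assumed true one. Read as an average at dispersion 1.6, it overstates borrowing by about 23 subjects per arm at 40% (123 against 100) and 37 at 45% (162 against 125). At 35% the difference is about 4. At no effect the average is about -22, not -42.

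Both are reporting corrections of low priority. Neither undermines the borrowing design.

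**What to change.** 1. In Protocol Table 7 and SAP Table 2, state the false-positive rate as about 12.8% at dispersion 2.0. Show 11.8% beside it as the value if the true dispersion is 1.6, and note that both depend on blinded estimates without stated precision.
2. If the blinded 2.0 is re-derived for one column, do it for all: dispersion about 1.87, 1.82 and 1.77 at 35%, 40% and 45%, with success about 78%, 87% and 94%.
3. In Protocol Table 9, either recompute the row as an average over the sampling distribution (about -22, 72, 100 and 125 at dispersion 1.6) or relabel it as the ESS when the observed rate ratio equals the assumed true one.

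The cost is a few restated figures in two matching tables and one recomputed or relabelled row. The stated figures become slightly less favourable. Sample size, prior weight and decision rule stay as they are.

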9.2.3. Sample Size Re-estimation or Adjustment

Blinded evaluation of exacerbation rates is planned for this study. A blinded evaluation of exacerbation rates for the purpose of sample size re-estimation will be done after 15 months of enrolment, or when 225 subjects have been randomized, whichever is earlier. If the exacerbation rates for the study are lower than planned, a sample size re-estimation may be conducted. Any subsequent change to the planned number of subjects randomized would be documented in a protocol amendment.

Prior to protocol amendment no 4, blinded evaluations of exacerbation rate indicated data that deviated substantially from the original assumptions for the study. These assumptions were based on data prior to the COVID-19 pandemic. The planned primary analyses is updated in order to maintain the planned sample size without further adjustment.

9.3. Data Analysis Considerations

The following analysis populations will be derived as required.

9.3.1. Analysis Populations

- All Subjects Enrolled Population**

The All Subjects Enrolled (ASE) Population will comprise all subjects enrolled and for whom a record exists on the study database. This population will be used summarizing reasons for screen and run-in failures.

- Modified Intent-to-Treat Population**

The Modified Intent-to-Treat (MITT) population will consist of all randomized subjects who receive at least one dose of trial medication and will be the primary population for all analyses of efficacy and safety data. 'Modified' implies that subjects who were randomized but did not receive study treatment were excluded.

- Per Protocol Population**

The Per Protocol (PP) population will consist of all subjects in the Modified Intent-to-Treat population not identified as full protocol deviators with respect to criteria that are considered to impact the primary efficacy analysis. The decision to exclude a subject from the PP Population or exclude part of their data from the PP Population analyses will be made prior to breaking the blind. This population will be used for a supplementary analysis of the primary endpoint.

- PK Population**

The PK population will comprise subjects in the PK sub study who received at least one dose of study medication and for whom at least one pharmacokinetic sample was obtained, and analyzed. This will be the primary population for assessing PK.

9.3.2. Interim Analysis

Blinded evaluation of exacerbation rates is planned for this study. This will be done under blinded situation and will not treated as formal interim analysis.

No formal interim analysis is planned.

9.4. Key Elements of Analysis Plan

The primary treatment comparison of interest in the study is mepolizumab 100mg SC vs placebo. This treatment comparison will be made for the primary and secondary endpoints. There is no adjustment for multiplicity for the secondary endpoints.

9.4.1. Efficacy Analyses

Bayesian Dynamic Borrowing Design

Bayesian dynamic borrowing (BDB) provides a clinically and statistically rigorous method to analyze this China bridging study. An explicit, pre-specified belief about the relevance of the global MEA115588 results to the Chinese population on treatment effect is provided as part of the prior distribution, which is a mixture with two components, one reflecting results from MEA115588 study and a vague component reflecting ‘no effect’.

The prior mixture will be updated with the China data to obtain the posterior distribution, which will also be a mixture. The posterior weight given to the global MEA115588 study data is commensurate with the strength of evidence of similarity between the MEA115588 data and the China data. The BDB analysis ‘learns’ how much of the global MEA115588 study information to borrow based on the consistency between the observed rate ratio in the China and global studies and updates the weight on the global MEA115588 results accordingly.

- The stronger the evidence of consistency, the greater the increase in the updated (posterior) weight on the informative component relative to the prior weight, and hence the greater the borrowing from the global study results.
- Conversely, if the China study results are very different to the global study results, the informative component is down-weighted and final inference is based mostly on the observed data in the China study alone.
- The mechanism by which the weight is updated is entirely pre-specified and mathematically rigorous ([Schmidli, 2014](#))

The informative prior and prior weight in BDB design

The BDB approach will use the results from the global MEA115588 study mixed with a vague component worth two subjects as an ‘informative’ but robust prior for the treatment comparison of interest in this China study. There are two primary analysis comparisons: mepolizumab 75mg IV vs placebo and mepolizumab 100mg SC vs placebo for rate of clinically significant exacerbations over the 32 weeks treatment period expressed as exacerbation rate per year in MEA115588. Since the primary outcome, rate of clinically significant exacerbation, showed similar treatment difference in Mepolizumab 75 mg iv group compared with placebo in 32-week Study MEA115588 and 52-week Study MEA112997, this indicates the available efficacy result of Mepolizumab 100 mg SC in 32-week study MEA115588 could also be an informative reference data to bridge to this 52-week China study using the same dose regimen, therefore, the results of mepolizumab 100mg SC vs placebo in study MEA115588 are used to build the global component.

Table 8 The primary analysis of clinically significant exacerbations results in global MEA115588 study

Treatment	No. subjects	Rate ratio (95% CI)	Normal distribution of Rate Ratio (log)	
			Mean	Standard Error
Mepolizumab 100mg SC	194	0.47 (0.35,0.64)	-0.7474	0.1532
Placebo	191			

Source: Table 13 in the CSR of MEA115588.

The logarithmic transformation of the rate ratio will be used, which can be approximately Normally distributed. Therefore, in the primary analysis for the primary treatment comparison of mepolizumab 100mg SC and placebo for the rate of clinically significant exacerbations of asthma over the 52-week treatment period in this study, the global prior component is obtained from the sampling distribution of the log rate ratio between mepolizumab 100mg SC and placebo in the global study MEA115588. The mean log rate ratio and its associated standard error are -0.7474 and 0.1532, respectively, leading to a normal distribution with mean -0.7474 and standard deviation 0.1532 as the global prior component for the primary treatment comparison.

A second vague distribution worth 2 subjects (one in each treatment arm) assuming no treatment effect in China will also be specified, to allow for the possibility that the global MEA115588 data do not provide relevant information about the treatment effect in Chinese patients. A normal distribution with mean zero and standard deviation 2.1256 will be used as vague prior for log rate ratio in BDB design, more details can be found in [Appendix 9 Section 12.9.2](#). A weighted combination of the ‘informative’ and ‘vague’ priors will be used to construct a robust mixture prior.

In the primary analysis, a prior weight of 50% is proposed for the informative component of the robust mixture prior, with the remainder of the weight (50%) placed on the vague component to reflect a conservative starting position regarding the assumed relevance of the global MEA115588 results to Chinese patients. See Statistical [Appendix 9 Section 12.9.2](#) for more details on the robust mixture prior and [Section 12.9.3](#) for details on the choice of prior weight.

Effective Sample Size

The updated weight itself is not directly interpretable as the fraction of the global MEA115588 study sample size that is borrowed. Instead, the effective sample size (ESS) borrowed from the global study can be quantified using the moment method implemented in RBesT R software package version 1.6.1, [Table 9](#) shows the expected value of the ESS borrowed from the global MEA115588 study for each treatment comparison when the true reduction in China is assumed to be 45%, 40%, 35% and 0 as the same with [Table 8](#).

Table 9 Expected Effective Sample Size borrowed per arm from the global MEA115588 study for a range of possible true treatment differences

	The true reduction			
	0	35%	40%	45%
Expected value of ESS borrowed per arm from the global MEA115588 study	-42	76	123	162

Maximum Detectable Value for Rate Ratio

The maximum detectable value (MDV) is the maximum rate ratio that needs to be observed in this China study in order to meet the pre-specified success criteria when combined with the global MEA115588 study results via the Bayesian dynamic borrowing analysis. Under the current sample size of 300 participants in total (256 evaluable participants and 44 subjects for drop out), assuming overall event rate is 0.78 p.a. based on the blinded evaluation and dispersion is 1.6, chosen weight on global component in the mixture prior of 0.5, and success rule that the posterior probability of the true rate ratio in China being less than 1 is at least 95%, the MDV for rate ratio between mepolizumab and placebo is 0.776. That corresponds to a minimum detectable reduction for mepolizumab compared with placebo of at least 22.4%.

